8.1 Analysis of MS Relapses

8.1.1 Relapse date imputations and handling of duplicate relapse records

The start date of a relapse should never be missing. However, missing or partial dates may be expected from some non-phase III trials where data checking may be less vigorous than in phase III trials. To avoid an artificial inflation of the number of relapses by low quality data, missing dates for relapses will only be imputed if the end date of the relapse is after the first dose of the initial study (i.e. if the relapse happened at least partially within the study). If partial or complete end dates are before the first dose date of the initial study, then no imputation will be done. If partial or complete relapse end dates are after the first dose of the initial study, the following algorithm will be applied:

Firstly, drop blanks and impute missing or partially missing start dates

1. Drop complete blanks: If the relapse onset date is invalid (e.g. “No”, “None”) or completely missing and there is no information recorded across all variables, the onset date will be set to missing.
2. Otherwise, if the record is not empty or the onset date is partially missing, check if another record may be available for the same relapse. Concretely:
 - a. If a relapse onset date has a missing day-part (XX-MM-YYYY), where XX represents the missing or invalid part, the onset date will be imputed by the onset date of another treatment-emergent relapse record with a non-missing start date for the same patient within the same month and year, if such a relapse is available (choose the first one if more than one is available).
 - b. If a relapse onset date has a missing day- and month part (XX-XX-YYYY), the onset date will be imputed by the onset date of another treatment-emergent relapse record for the same patient within the same year, if such a relapse is available (choose the first one if more than one is available).

3. Otherwise, if the onset date of a relapse is completely or partially missing, the onset will be imputed with the first possible day within the available non-missing date-part, or the first-dose date, or the relapse end-date minus 90, whatever occurs latest.

Secondly, impute the end date

The imputation of missing or partially missing end dates will be done after the imputation of start dates.

1. If the end date of a relapse is completely missing, it will be imputed as 90 days after the onset date.
2. If the end date of a relapse is partially missing, it will be imputed as the maximum of the relapse start day plus one or the minimum of either 90 days after the onset date, or as the last possible day based on the non-missing parts of the end-date (e.g. XXDEC2007 where XX indicated the missing end day would be imputed as 31-DEC-2007 if the onset date of the relapse was 26-NOV-2007).

Thirdly, handle duplicate relapse records:

After the imputation of start and end-dates is completed, records which refer to the same relapse (30-day rule) will be combined into a new artificial record. This step will help to consolidate core and extension databases where the same relapse may be recorded more than once, and it will help to ensure consistent relapse rules even for studies with a less vigorous date management.

1. For each patient relapses will be sorted by onset date (source or imputed).
2. **Combine relapses for which the distance between onset dates is <30 days:** Starting from the first relapse within each patient, the distance from each relapse to the next will be tested. If the onset date of a relapse is less than 30 days from the onset date of a previous one, an artificial record will be created using the “worst” or “most severe” information from both records (Conservative approach). The following rules apply:
 - a. Onset date: use the *minimum* of the candidate dates with the highest degree of completeness. The degree of completeness is defined in descending order: 1. Original date, 2. Only day-part imputed, 3. Day and Month part imputed, 4. Day, Month and Year imputed.

Example: an original date entered by the investigator has the higher degree of completeness compared to a partial/imputed date. An imputed date with just the day-part imputed has the higher degree of completeness compared to a completely imputed date. Rationale: amongst the candidate-dates with the highest reliability/completeness – choose the first/worst.
 - b. End date: use the *maximum* of the candidate dates with the highest degree of completeness. The degree of completeness is defined in descending order: 1. Original date, 2. Only day-part imputed, 3. Day and Month part imputed, 4. Day, Month and Year imputed.

Example: an original date entered by the investigator has the higher degree of completeness compared to a partial/imputed date. An imputed date with just the day-part imputed has the higher degree of completeness compared to a completely imputed date. Rationale: amongst the candidate-dates with the highest reliability/completeness – choose the last/worst.

- c. When two records are combined from two consecutive phases (e.g. one from an initial study, the other one from an extension) the combined record will be considered as belonging to the first phase.

Example: A relapse may have started at the end of an extension but ended in an Umbrella study. The same relapse may then be captured in the extension and also in the Umbrella study. When the two records are combined into one, the relapse – according to its start date – will be considered in the extension phase. Programmatically: Ext1n will take the minimum value of the two combined records.

- d. Hospitalization: “yes” is worse than “no”
- e. Severity: “severe” is worse than “moderate” is worse than “mild” is worse than “unknown”
- f. Steroids: “yes” is worse than “no”
- g. Relapse confirmed: “yes” is worse than “no”
- h. Recovery: “none” is worse than “partial” is worse than “complete”
- i. Daily activity: “affected” is worse than “not affected”

Lastly, truncate the duration of all relapses to a maximum of 90 days

1. For each relapse record, check whether the duration from onset to end date is less or equal to 90 days, if this is not the case do the following:
 - a. Determine the degree of completeness of the start and end-date. The degree of completeness is defined in descending order: 1. Original date, 2. Only day-part imputed, 3. Day and Month part imputed, 4. Day, Month and Year imputed.

Example: an original date entered by the investigator has the higher degree of completeness compared to a partial/imputed date. An imputed date with just the day-part imputed has the higher degree of completeness compared to a completely imputed date.
 - b. Keep the date with the higher degree of completeness fixed and update the other date, so that the duration the relapse is maximized to 90 days.

Rationale: If one of the dates has to be replaced to keep truncate the duration of the relapse to 90 days, keep the date with the higher degree of completeness/reliability fixed (either the end- or the start date) and replace the other one.
 - c. If the onset- and end-date have the same degree of completeness, keep the start date fixed and impute the end-date such that the duration of the relapse is maximized to 90 days.
2. If a relapse is recorded as ongoing at the final exam, impute an end date such that the duration is maximized to 90 days.

8.1.2 Annualized relapse rates

Annualized relapse rate (ARR) is defined as the *number of relapses* experienced during a specific period of time adjusted to a one-year period. The ‘number of relapses’ can refer to

either the number of *confirmed relapses* or the number of *all relapses* (including both confirmed and unconfirmed relapses).

Confirmation of relapses is not collected in the following studies: CFTY720D2316, CFTY720D2320, CTY720D2399E1, and the long-term follow-up study prior to protocol amendment 4. Therefore, the number of confirmed relapses during this time is not able to be reported. Additionally, confirmed relapses will not be reported for patients from the CFTY720D2324 study since it is a phase IIIb study and confirmation is not collected in the long-term follow-up study for patients coming from previous studies that are not phase II/III. The number of unconfirmed relapses is also not able to be reported for study CTY720D2399E1 since the study does not collect relapse start dates. However, note that the time during which number of relapses is not able to be counted and the time off study for patients who re-enrolled into the long-term follow-up study will still be included in the time in study, which can make the ARR appear lower than it actually is. If confirmation of a relapse is missing or not collected, the relapse will be treated as an unconfirmed relapse. Therefore, ARR based on all relapses (confirmed or unconfirmed) should be considered a more reliable estimation of relapse rate than ARR based on confirmed relapse.

The group level (aggregate) ARR will be calculated as follows: (total number of relapses) / (total number of days in the study for all patients for that specific period of time) x 365.25.

8.1.3 Time in study

For the analysis of ARR from first dose of fingolimod to end of study treatment, the time in study (days) is calculated as: last dose date of fingolimod – first dose date of fingolimod among all studies + 1 day. Similarly, the time in study from first dose of fingolimod among all studies to end of follow-up is calculated as: last available visit/evaluation date across all panels – first dose date of fingolimod among all studies + 1 day.

For the analysis of ARR from first dose of fingolimod among all studies to end of a particular month (i.e. “Month 6”, “Month 12”, “Month 24”, and every 12 months from then on), “Month 0 to X” time in study will be calculated as minimum of (first dose date of fingolimod + integerpart(X/12*365.25) where X denotes the month, last available visit/evaluation date across all panels) – first dose date of fingolimod + 1 day.

8.1.4 MS relapses analyses

MS relapses analyses will be conducted on the fingolimod full analysis set. All analyses will be done for all relapses (confirmed and unconfirmed) and for confirmed relapses.

A summary of ARRs will be presented by time period (cumulative time intervals: ‘Month 0 to Month 6’, ‘Month 0 to Month 12’, ‘Month 0 to Month 24’, ‘Month 0 to Month 36’, ... incremented by 1 year for each successive interval, plus ‘Month 0 to end of study treatment’ and ‘Month 0 to end of follow-up’) from first dose of fingolimod among all studies. The summary will include number of patients summarized, number of relapses, time in study (days), and group level ARR. In addition, model based estimates of ARR and corresponding two-sided 95% confidence interval will be obtained by fitting a negative binomial regression model adjusted for the number of relapses in the last two years prior to enrolment in the core

study and EDSS score at first dose of fingolimod baseline, with the logarithm of the time in study as the offset variable.

A summary of relapse characteristics will be displayed by time period (consecutive yearly intervals: ‘Month 0 to Month 12’, ‘Month 12 to Month 24’, etc., plus ‘End of study treatment to End of follow-up’) from first dose of fingolimod among all studies. Relapse characteristics will be summarized at a patient level (the number and percent of patients with at least one relapse type) and at a relapse event level (the number and percent of a particular type of relapse out of the total number of relapses). The types of relapses being summarized include: relapses which affect daily activities, relapses which require steroids, and relapses which require hospitalization.

The time to first onset of relapse from first dose date of fingolimod among all studies will be analysed. Specifically, the number of patients at risk, the cumulative number of patients with relapse, the Kaplan-Meier (KM) estimate of the percent of patients without relapse and corresponding standard error and two-sided 95% CI will be provided at each yearly time point (1 year = 360 days). Patients with no relapse, patients for whom follow-up ends before a confirmed relapse occurs, and patients who drop out prior to the relapse will all be censored, i.e. the time to event for these patients will be the time in study (from first dose of fingolimod among all studies to last available visit/evaluation date across all panels).

A Kaplan-Meier plot of time to first relapse from first dose of fingolimod to end of the study part 2 will be presented.

9 Safety evaluation

The primary objective of this study is to evaluate the long-term safety and tolerability of fingolimod 0.5 mg in patients with relapsing forms of MS.

Long-term safety will be assessed in terms of adverse events (AEs), pregnancy tests, vital signs (including dose administration monitoring), and electrocardiograms (ECG) dose administration monitoring.

9.1 Adverse events

9.1.1 Imputation of adverse event start date

Missing or partial adverse event start dates are imputed following the VDW MAP Module 8 ‘Adverse Event Start Date Imputation (#IMPUTA EV)’ section (displayed below):

Adverse Event Start Date Imputation (#IMPUTA EV)

The following table explains the notation used in the logic matrix. Please note that **missing start dates** will not be imputed.

Note, it may happen that the imputed AE start is after AE end date. Missing AE end date is not imputed by STL.

	Day	Month	Year
Partial Adverse Event Start Date	Not used	MON	YYYY

Treatment Start Date (TRTSTD)	Not used	TRTM	TRTY
--------------------------------------	----------	------	------

The following matrix explains the logic behind the imputation.

	MON MISSING	MON < TRTM	MON = TRTM	MON > TRTM
YYYY MISSING	NC	NC	NC	NC
YYYY < TRTY	(D)	(C)	(C)	(C)
YYYY = TRTY	(B)	(C)	(A)	(A)
YYYY > TRTY	(E)	(A)	(A)	(A)

The following table is the legend to the logic matrix.

Relationship	
Before Treatment Start	Partial date indicates AE start date prior to Treatment Start Date
After Treatment Start	Partial date indicates AE start date after Treatment Start Date
Uncertain	Partial date insufficient to determine relationship of AE start date to Treatment Start Date
Imputation Calculation	
NC / Blank Uncertain	No convention
(A) After Treatment Start or Uncertain	MAX(01MONYYYY, TRTSTD+1)
(B) Uncertain	TRTSTD+1
(C) Before Treatment Start	15MONYYYY
(D) Before Treatment Start	01JULYYYY
(E) After Treatment Start	01JANYYYY

9.1.2 Adverse events analyses

All adverse events (AEs) recorded on the adverse events CRF will be coded using the current Medical Dictionary for Regulatory Activities (MedDRA). Note that adverse events that started or were ongoing during any gap between the completion of the prior study (part 1) and enrollment into this CFTY720D2399 study part 2 can be recorded on the CFTY720D2399 part 2 adverse events CRF.

In AE summaries, primary system organ classes will be displayed in alphabetical order and preferred terms (within each system organ class) will be sorted by descending frequency.

There are two categories of AE summaries in this study: AEs during the long-term follow-up study part 2 and AEs during the fingolimod treatment period.

9.1.2.1 Adverse events during the study part 2

Only AEs captured in CFTY720D2399 study part 2 database will be summarized. Unless otherwise specified, all non-serious adverse events recorded in the CFTY720D2399 part 2 database with an onset at any time from first dose date of fingolimod among all studies to last dose date of fingolimod + 45 days are included. All serious adverse events (SAEs) recorded in the CFTY720D2399 part 2 database with an onset at any time from first dose date of fingolimod among all studies are also included in the summaries.

Adverse events reported during the study part 2 will be summarized for the safety set.

There are two subcategories of AE summaries during the study part 2 as below.

9.1.2.1.1 Occurrence of adverse events

Adverse events reported during the study part 2 will be summarized by primary system organ class (SOC) and preferred term (PT), and will show the number and percentage of patients with at least one adverse event in each SOC or PT category. Similarly, adverse events by study drug relationship (AEs suspected to be study drug related, AEs not suspected to be study drug related, and AEs regardless of study drug relationship), AEs by severity (mild, moderate and severe), SAEs, SAEs by study drug relationship, SAEs by severity, suspected study drug related AEs, and AEs leading to study drug discontinuation will also be summarized by SOC and PT.

When subjects had AE occurrence on same PT for more than once, but with different relationship, the subject will be counted in each category of relationship. When severity are different, subject will only be counted once in maximum severity of that PT.

AEs and SAEs which are not considered to be known effects of fingolimod treatment (i.e., excluding those listed in the most recent version of Core Data Sheet), will be summarized by PT only. To determine which AEs occur after discontinuation of fingolimod treatment, all AEs reported with onset date after the last dose of fingolimod until the end of the study part 2 will be summarized by SOC and PT for the follow-up set.

To determine which AEs have occurrence after study part 2 enrollment, newly-occurring AEs will be summarized by SOC and PT for the safety set. A newly-occurring AE is defined as an AE which starts after part 2 informed consent date. A similar summary will be provided for SAEs.

Principal cause of death during the study part 2 will be summarized by SOC and PT. All deaths recorded in the CFTY720D2399 part 2 database with onset on or after the first dose date of fingolimod (among all studies) will be included in the summary.

All information pertaining to any AE with severity information, SAEs, AEs leading to study drug discontinuation, deaths and neoplasms system organ class events that reported during the study part 2 will be listed for the safety set. Additionally, adverse events, SAEs and all deaths recorded during the study part 2 will be listed for the subgroup of patients from studies D2312 and D2402 in the enrolled set.

9.1.2.1.2 Incidence rate of adverse events

The AE incidence rate (IR) is calculated per 100 patient-years. IR is defined as: the number of patients experiencing at least one event in a particular category, over the total patient-years of the “at risk” population for that event multiplied by 100. An underlying Poisson process for incidence rate within treatment group is assumed. For the summary time period for extension part 2, only AEs with a start date between first dose date of fingolimod during the study part 2 and the last dose date of fingolimod + 45 days will be counted; or SAEs with a start date on or after first dose date of fingolimod during the study part 2 will be counted.

To calculate the total patient-years (time at risk) of the “at risk” population:

1. For patients who have a particular AE category, sum the number of days from first dose date of fingolimod during the study part 2 to the first occurrence of that particular AE category
2. For patients who did not have a particular AE category, sum the number of days from first dose date of fingolimod during the study part 2 to last dose date of fingolimod + 45 days.
3. Add the time at risk for patients who had a particular AE category with the time at risk for patients who did NOT have a particular AE category. This is the total time at risk of that AE category.
4. Divide the total time at risk by 365.25.

Incidence rate of adverse events will be presented for the safety set. Incidence rate of AEs, AEs by relationship, excluding AE listed in the core data sheet, will be presented by PT. Similarly, all above indicated AE IR summaries will be conducted for SAEs.

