## **9 Data analysis**

Unless otherwise mentioned, all data collected from the first dose of fingolimod in the original core/extension studies, if available, and in this long-term follow-up study will be analyzed to evaluate the long-term safety, tolerability, and effectiveness of fingolimod 0.5 mg/day in patients with MS. The baseline relative to the first dose of fingolimod (FDF baseline) will be used where change from baseline is analyzed. All the summaries will be provided by the highest assigned fingolimod dose, (i.e., fingolimod 0.5 mg/day) and any dose of fingolimod.

During Study Part Two, only adverse events, first dose monitoring, vital signs, Ophthalmological exam/OCT, and relapse are collected. The analysis including data from Study Part Two will be specified in the relevant sections.

The follow-up data after discontinuation of the study treatment in Study Part One or Study Part Two will also be summarized where appropriate.

Summary statistics for continuous variables will include N, mean, standard deviation, minimum, lower quartile, median, upper quartile and maximum.

Summary statistics for discrete variables will be presented in terms of absolute and relative frequencies. AE incidence adjusted by exposure is also used to evaluate the risk over time and presented as number of patients experiencing at least one event per 100 patient years of the at-risk population.

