## **9.4 Analysis of the primary variable(s)**

### **9.4.1 Variable**

Long-term safety will be assessed based on adverse events (AEs), laboratory and vital signs as well as other investigations performed when clinically indicated.

Analysis of the safety variables will be conducted on

[figure not shown]
- Safety set: for any analyses including data collected during the long-term follow up study only
- Fingolimod safety set: for analyses including data from first dose of fingolimod in the original core/extension study, if there is any, and in the long-term follow up study.

Given the nature of the design, the data will be presented using descriptive statistics and no inferential analyses are planned.

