#### **9.4.1.1 Adverse events (AEs)**

Incidence rates (IRs) of adverse events per 100 patient-years will be summarized by highest assigned fingolimod dose (fingolimod 0.5 mg/day and any dose of fingolimod) based on the fingolimod safety set.

To further evaluate the risk with longer fingolimod exposure duration, adverse events reported with different fingolimod exposure durations will be assessed based on the fingolimod safety set.

In addition, the incidence of adverse events (new or worsened from the long-term extension baseline) reported during the long-term follow up study will be summarized by primary system organ class and preferred term as frequency count and percentage of patients with adverse events based on the safety set.

- Any adverse events
- Serious adverse events (SAEs)
- Suspected study drug related adverse events
- Adverse events leading to discontinuation
- Deaths

All information pertaining to serious adverse events and deaths noted during this study will be listed by center and patient number.

The same analysis including data collected during the Study Part Two will be conducted for the subgroup of patients who entered Study Part Two.

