9.1.2.2 Adverse events during the fingolimod treatment period

Unless otherwise specified, all non-serious adverse events with onset on or after first dose date of fingolimod among all studies to last dose date of fingolimod + 45 days are included. All serious adverse events (SAEs) with onset on or after the first dose date of fingolimod among all studies are also included in the summaries. Also, unless otherwise specified, adverse events will be summarized for the fingolimod safety set, by primary system organ class and preferred term, and will show the number of patients with at least one adverse event and the incidence rate of adverse events per 100 patient-years in each SOC or PT category.

The AE incidence rate (IR) is calculated per 100 patient-years. IR is defined as: the number of patients experiencing at least one event in a particular category, over the total patient-years of the “at risk” population for that event multiplied by 100. An underlying Poisson process for incidence rate within treatment group is assumed.

To calculate the total patient-years (time at risk) of the “at risk” population:

1. For patients who have a particular AE category, sum the number of days from first dose date of fingolimod among all studies to the first occurrence of that particular AE category

2. For patients who did not have a particular AE category, sum the number of days from first dose date of fingolimod among all studies to last dose date of fingolimod + 45 days.
3. Add the time at risk for patients who had a particular AE category with the time at risk for patients who did NOT have a particular AE category. This is the total time at risk of that AE category.
4. Divide the total time at risk by 365.25.

Incidence rate of adverse events will be presented for the fingolimod safety set and for the subgroup of fingolimod safety set patients from phase II/III studies, by SOC and PT. Incidence rate of AEs, excluding AE listed in the core data sheet, will be presented by PT. Incidence rate of AEs that fulfill the risk search term (defined in the case retrieval sheet) will be presented by risk name and lower level terms. Similarly, all above indicated AE IR summaries will be conducted for SAEs.

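### The Part 2 SAP omits the protocol's adverse-event incidence rate from first fingolimod dose, and its replacement is not comparable with the Part I rate

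*SAP*

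**What the plan says.** **Protocol.** Section 9 sets the default window: "all data collected from the first dose of fingolimod in the original core/extension studies, if available, and in this long-term follow-up study will be analyzed". Section 9.4.1.1, under the primary variable, plans AE incidence rates per 100 patient-years by highest assigned dose, the two groups being 0.5 mg/day and "any dose of fingolimod) based on the fingolimod safety set". Section 9.4.1 says what that set is for: "Fingolimod safety set: for analyses including data from first dose of fingolimod in the original core/extension study". Section 9.4.1.1 then ends with a paragraph of its own: "The same analysis including data collected during the Study Part Two will be conducted for the subgroup of patients who entered Study Part Two".

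**Part I SAP, 9.1.2.2.** Time at risk follows the protocol. For patients with the event, "sum the number of days from first dose date of fingolimod among all studies to the first occurrence of that particular AE category".

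**Part 2 SAP, 9.1.2.1.2.** This section holds the only incidence rate in the Part 2 plan. For patients with the event, "sum the number of days from first dose date of fingolimod during the study part 2 to the first occurrence of that particular AE category". It counts "only AEs with a start date between first dose date of fingolimod during the study part 2 and the last dose date of fingolimod" plus 45 days, and SAEs from the first Part 2 dose onward. The population is the safety set. Section 2.1 shows a single dose group throughout, except that AEs by yearly interval also get a version for patients whose highest dose was 0.5 mg. Section 9.1.2.2 keeps the first-fingolimod-dose origin, but reports numbers and percentages of patients per 360-day interval.

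**The concern.** Protocol 3.1 says Part Two collects further long-term safety data in support of the primary objective. The exposure-adjusted rate covering the longest follow-up is the analysis that the Part 2 plan leaves out, and it gives no reason. No other plan fills the gap: the Part I SAP stops at the end of Part I and, in 2.3.1, leaves Part II to a separate document.

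The rate that replaces it carries the same name, nearly the same four-step calculation and the same unit as the Part I rate, but it estimates something else. Part I measures the first event since starting fingolimod. Part 2 measures the first event since entering Part 2, so a patient who had the event in an earlier year is put back at risk. Section 9.1.2.1.2 does not say how such patients enter the at-risk population, although section 2.5 notes that AEs continuing from Part 1 may sit in the Part 2 database. Anyone who sets the two reports side by side would be comparing different quantities.

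**Working it through.** The documents give no numeric incidence rate and no sample size calculation, so there is no planned figure to reproduce. The check has two parts.

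**1. The definitions side by side**

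| | Protocol 9.4.1.1, Part Two entrants | Part I SAP 9.1.2.2 | Part 2 SAP 9.1.2.1.2 |
|---|---|---|---|
| Clock starts | First fingolimod dose | First fingolimod dose, all studies | First Part 2 dose |
| Event counted | First since fingolimod start | First since fingolimod start | First since Part 2 start |
| Set | Fingolimod safety set | Fingolimod safety set | Safety set |
| Dose groups | 0.5 mg and any dose | 0.5 mg and any dose | One |

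The Part 2 SAP does define a fingolimod safety set (2.5) but assigns no incidence rate to it. It keeps the first-dose clock for relapse rates (8.1.3), a secondary variable.

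**2. How far the two rates can differ**

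The SAPs define the rate as patients with a first event divided by time to that event or end of window. For a window of T years its expected value is

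IR(T) = 100 × (1 − S(T)) / ∫₀ᵀ S(t) dt, where S(t) is the probability of no event by time t.

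Inputs from the documents: Part Two lasts about 2 years (protocol 3.2), total exposure is 7–15 years (3.3), and both SAPs assume an underlying Poisson process. Assumptions not in the documents: 7 years from first fingolimod dose to Part 2, event rate λ of 0.01 to 0.5 per year, between-patient variance θλ² with θ up to 2, and no dropout.

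*(a) One constant rate for everyone.* S = exp(−λt), so IR = 100λ for any T, and the ratio of the 2-year to the 7-year rate is 1.00. A simulation of 200,000 patients at λ = 0.2 gave 19.98 and 20.03 per 100 patient-years.

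*(b) Recurrent event; each patient's rate is constant, but rates vary between patients (gamma).* S = (1 + θλt)^(−1/θ). For θ = 1 the integral is ln(1 + λT)/λ. With λ = 0.2:
- T = 2: (1 − 1/1.4) / (ln 1.4 / 0.2) = 0.2857 / 1.682, or 16.98 per 100 patient-years.
- T = 7: (1 − 1/2.4) / (ln 2.4 / 0.2) = 0.5833 / 4.377, or 13.33. Ratio 16.98/13.33 = 1.27.
- T = 9, the cumulative window the protocol asks for: (1 − 1/2.8) / (ln 2.8 / 0.2) = 0.6429 / 5.148, or 12.49. Ratio 1.36.

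*(c) Event that cannot recur, with earlier cases kept in the Part 2 denominator.* With λ = 0.2, new cases = exp(−1.4) − exp(−1.8) = 0.2466 − 0.1653 = 0.0813. Person-years = 0.0813/0.2 + (1 − 0.2466) × 2 = 0.4065 + 1.5068 = 1.913. The rate is 4.25 against 20.0, a ratio of 0.21.

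Ratio of the restarted 2-year rate to the 7-year rate:

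| λ per year | (a) common rate | (b) recurrent, θ 0.5 to 2 | (c) non-recurring |
|---|---|---|---|
| 0.01 | 1.00 | 1.01–1.05 | 0.93 |
| 0.05 | 1.00 | 1.06–1.19 | 0.69 |
| 0.2 | 1.00 | 1.15–1.45 | 0.21 |
| 0.5 | 1.00 | 1.22–1.63 | 0.02 |

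The length of prior exposure matters too. In (b) with λ = 0.2 and θ = 1 the ratio is 16.98/14.43 = 1.18 against a 5-year window and 1.57 against 15 years.

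*(d) Early-onset event.* Protocol Appendix 7 gives macular edema in 0.4% of patients on 0.5 mg/day, about 75% of it within 3–4 months. Assume that 0.4% covers 7 years, that 75% falls in the first 4 months, and that the rest is spread evenly. The rate from first dose is then 100 × 0.004/7 = 0.057, and the late-period rate is 100 × 0.004 × 0.25/(7 − 1/3) = 0.015, a ratio of 0.26. Here risk does change over time, so this is not an unchanged-risk case. It shows only that the two rates can also differ in the other direction.

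**The case against.** *The protocol's closing sentence may refer only to the in-study AE counts listed just above it.* This is possible but weak. The sentence is a separate paragraph closing a section that opens with the incidence rate, and protocol section 9 makes data from first fingolimod dose the default.

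*The yearly tables already cover late risk.* In part they do. They run from first fingolimod dose through Part 2, use interval-specific denominators, include the risk search terms, and have a highest-dose 0.5 mg version. They meet the protocol's separate request to look at AEs by exposure duration, and they show late years more directly than one cumulative rate would. But they do not adjust for exposure: a patient with one day in an interval counts in the denominator like one with 360 days. They are not the rate per 100 patient-years that the protocol names.

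*The window is stated, the study is descriptive, and no comparison of the two rates is planned.* All true. The section does say that its period is Part 2. That makes a wrong reading less likely, but it does not supply the missing analysis.

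*A stronger reading is tempting: that restarting the clock makes unchanged risk look higher in Part 2 and so creates a false late safety signal.* The documents do not support it. Under the SAPs' Poisson assumption with a common rate, the expected rates are equal. The Part 2 rate is higher only for recurrent events in patients who differ in rate, and for rare events that excess is small. For non-recurring or early-onset events it is lower, so late risk could be understated. Selection may also lower it, because protocol 4.2 excludes patients who permanently discontinued an earlier fingolimod study for an AE. A reader might also infer that a cumulative rate was the main reason to extend the study. Amendment 10 and protocol 3.2 give continued drug access as the main reason, with safety data collected alongside.

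**Conclusion.** The omission stands on the text alone and needs no modelling. The protocol calls for the AE incidence rate from first fingolimod dose in Part Two entrants, by two dose groups, and the Part 2 SAP has no such analysis and does not explain its absence.

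The second conclusion is that the Part I and Part 2 incidence rates are not comparable. No single direction or size can be given. On the assumptions above, the ratio of the Part 2 to the Part I rate runs from 0.02 (a common event that cannot recur) through 1.00 (one constant rate) to 1.63 (a common recurrent event with strong differences between patients). At 0.01 per year it stays between 0.93 and 1.05. The event rates, the spread between patients and the 7-year window are assumed, and dropout and selection into Part 2 are left out. The ratios therefore show direction and range, not a forecast.

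**What to change.** In the Part 2 SAP, section 9.1.2, add AE and SAE incidence rates per 100 patient-years from first fingolimod dose among all studies to the end of Part 2. Use the time-at-risk method of Part I SAP 9.1.2.2, the fingolimod safety set already defined in Part 2 SAP 2.5, and the two dose groups, highest dose 0.5 mg and any dose.

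Keep the Part-2-only rate as a supplement, titled 'first event since Part 2 start'. State in 9.1.2.1.2 that patients with an earlier event in the category are in its risk set, and footnote the table as not comparable with the Part I rate.

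The cost is SAP wording and one extra table set. The method and the analysis set are already written. The Part 2 SAP is dated 26 November 2018 and plans database lock around December 2018 or January 2019, so the wording should be settled before lock.
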